The Importance of Assessing Suicide-Related Outcomes. Although the treatment target of BCBT is suicidal ideation and behavior, we will also assess psychiatric distress and suicide-related thoughts to characterize the sample and explore any ancillary treatment effect. It is important to assess concomitant treatments in any treatment outcome study to provide a context for interpretation of study results. In addition, assessment of service utilization will provide a confirmation of patient engagement with continuing care as well as indicate whether or not crisis services (ED, psychiatric readmission) were accessed.

Specific Aims/Hypotheses

As a pilot feasibility open trial, this study is not powered for statistical significance. However, we outline our predictions here in relation to descriptive statistics and/or effect sizes.

Aim 1: To describe the feasibility, acceptability, and tolerability of app-enhanced BCBT. Feasibility will be assessed using enrollment rates as well as a qualitative assessment of treatment implementation barriers and patient and clinician feedback. Acceptability will be assessed using the Client Satisfaction Questionnaire and app-user feedback. We expect that participants will continue to engage with the treatment after discharge via the SmartPhone App, as assessed using the Utility of Techniques Questionnaire and utilization data (e.g., number of times accessed) collected by the app. Tolerability will be assessed using rates of discontinuation and adverse events. We predict that descriptive data will demonstrate good feasibility, acceptability, and tolerability.

Aim 2: To collect initial descriptive pilot data and BCBT effect size estimates from pretreatment through follow-up for reducing suicidality and improving other suicide-related-outcomes. We predict that participants will demonstrate a large reduction in suicidal ideation from pretreatment to each follow-up assessment as evidenced by a Hedges' g of 0.8 (large effect) or greater. Effect sizes for changes in suicide-related outcome measures (psychiatric distress, suicide-related cognitions, service utilization) will also be explored. We predict that descriptive data will show low levels of suicidal behavior and psychiatric readmission over follow-up. For exploratory purposes, we will also assess other types of service utilization over follow-up (e.g., outpatient, ED visits).

Research Design

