Sampling. We will enroll 4 young adults (ages 18-24) admitted for inpatient treatment with a history of suicide attempt (lifetime) and active ideation (with or without plan or intent) on admission who own and have access to their phone (iPhone or Android with capability to

download apps) during their inpatient stay. Admission will be defined as admission to either the medical floor (in cases where medical stabilization was required following a suicide attempt) or to the psychiatric inpatient unit (in cases where medical stabilization was not required). Suicide attempt will be defined as self-directed behavior that results in injury or the potential for injury, and in which there was evidence, whether implicit or explicit, of intent to die. Inclusion criteria will also include ability to understand the nature of the study and provide written informed consent, willing and able to provide at least two verifiable contacts for emergency or tracking purposes, and expected length of stay long enough to complete the entire treatment protocol. Participants will be excluded if they are not fluent in English, are experiencing current mania or psychosis, have lifetime history of schizophrenia spectrum disorder, intellectual disability, or organic brain illness, if the inpatient treatment plan includes detox protocol or electroconvulsive therapy, or any other psychiatric or medical condition that in the investigator's opinion would preclude informed consent or participation in the trial. Participants who are not fluent in English will be excluded given that at least some assessments are available in English only, the research is utilizing an app only available in English and treatment is not validated using a translator. We expect that all enrolled participants will complete at least one treatment session; however, if there is attrition prior to completing at least one treatment session we will continue to enroll additional participants until we meet this target sample.

Measures. The Measurement Schedule is outlined in Table 1 and measures are detailed below.

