Treatment Acceptability and Implementation. **Implementation.** All study staff will track barriers encountered during study implementation via the Implementation Barriers Log. The log has been used in our previous suicide prevention studies and allows for tracking of logistical barriers to the study and treatment including room and participant availability. The Implementation Barriers Log has been adapted from our previous study to allow for descriptions of any technical difficulties or issues encountered with the SmartPhone app. Within session compliance will be tracked using the CBT Compliance Measure (CCM), a 9 item measure that assesses participant’s adherence to the session protocol (Wootton et al., 2021). Sample items include “To what extent did the patient’s words and actions in session adhere to the session agenda?” Responses are rated on a 4 point scale (*not at all* to *very much*) and are rated by the study therapist at the conclusion of each study treatment session. **App Use.** The System Usability Scale (SUS) is a valid and reliable 10-item measure that can be used to effectively differentiate between usable and unusable systems (Brooke, 1996; Dexheimer et al., 2017). Sample items are “I think that I would like to use this app frequently” and “I felt very confident using the system.” Responses are rated using a 5-point (*strongly disagree* to *strongly agree*) Likert scale. Total scores range from 0 to 100. A score of 68 is the minimal indicator of usability. Participants will also provide qualitative feedback about app use (e.g., Did you think functions were missing in the app? Which ones? Is there anything else you think we should know to make this app better?) at each study visit occurring after downloading the app. Data on app utilization (e.g., number of times accessed) will also be collected via the app. **Treatment Satisfaction.** Overall treatment satisfaction will be assessed using the Client Satisfaction Questionnaire (CSQ), an 8-item self-report assessing perceived quality and effectiveness of services, satisfaction with services, whether participants would return for similar treatment, and whether they would recommend this treatment to others (Nguyen et al., 1983). There is also a space for comments where the participant can write additional qualitative feedback. Each quantitative item is rated from 1 to 4 with higher numbers indicating higher satisfaction. The CSQ demonstrates good internal consistency and correlates with alternative satisfaction measures (Attkisson & Greenfield, 1999). **Qualitative feedback.** Additional qualitative feedback from the participant will be obtained regarding app usability and suggestions for changes to the treatment program overall. The clinician will also provide feedback on the treatment sessions and make suggestions for how to

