
improve the treatment program overall. **Treatment Utility.** The Utility of Techniques (UT) questionnaire, which we developed and are using in our ongoing adult RCT, will assess frequency of use (rated “*not at all*” to “*more than 10 times per week*”) and helpfulness (completed only if skill was used, rated “*not at all*” to “*extremely*”) of each treatment component.

Adverse Events. As in our ongoing research, adverse events will be assessed at every study visit using the questions “Have there been any changes to your physical health since the last time we met?” and “Have there been any changes to your mental health since the last time we met?” Adverse events will be tracked and reported according to IRB’s policy 910.

Service Utilization. Prescribed medication at intake and discharge will be determined through the electronic medical record. Assessments at each follow-up will also track changes in medication. Service utilization will also be assessed at each follow-up assessment using a modified version of the Cornell Service Index Short Form (CSI-SF; Sirey et al., 2005) and using a query of the HHC electronic medical record to determine changes in prescribed medications, as well as the number of encounters recorded for ER visits, outpatient behavioral health, and inpatient behavioral health (including length of stay).

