Procedure. Participants will be identified through electronic medical record review of daily admissions, and attending physicians will be consulted about each eligible participant to ensure study criteria are met and study participation is supported. Participants will provide written consent prior to initiation of study procedures. Assessments will be performed at intake, discharge, and 1-, 2-, and 3-months post-discharge. In the event that patients are discharged prior to completing this assessment, the assessment will be completed by phone and remote data collection as will be done for all follow-up assessments. Participants will complete up to 4 BCBT sessions (depending on length of stay). BCBT sessions will typically be administered once daily, but also with flexibility. In cases where the patient is discharged earlier than expected and prior to completing all treatment sessions, two sessions may be completed in the same day and/or the all-skills review may be incorporated into whatever session is final in order to cover as much treatment material as possible prior to discharge. In cases where the session material is not completed in one meeting, additional meetings will be scheduled in order to cover all session material. Assessments and treatment sessions will be audio-recorded. Self-reports will be collected through the HHC REDCap data system. Follow-ups will be completed using telephone interview and REDCap surveys. No study assessment measures are collected using the app.

Risk Management Procedures. Suicide risk will be assessed at every post-treatment study visit. A comprehensive risk management protocol is in place for managing suicidal symptoms based upon severity (low, medium, high-not imminent, high-imminent) in our current RCT and will also be used in this pilot study.

Statistical Analysis Plan

Analytic Plan. Descriptive statistics will be used to summarize quantitative (mean, standard deviation) and qualitative (frequencies) data for the following variables: recruitment and retention rates, implementation barriers, CSQ, treatment utilization (UTQ and app-derived utilization metrics), adverse events, service utilization (obtained from electronic medical record and CSI-SF), and suicidal behaviors. In addition to descriptive statistics, we will determine an effect size estimate Hedges's g for changes from intake to post-treatment and through follow-up for suicidal ideation, psychiatric distress, and suicide-related cognitions.

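### Mean and SD are the only summary named for quantitative data, so with four participants one heavy user can dominate the app-access and encounter counts

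*Combined protocol and SAP*

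**What the plan says.** The Analytic Plan (Statistical Analysis Plan) names one summary per type of data. Descriptive statistics will "summarize quantitative (mean, standard deviation) and qualitative (frequencies) data". The variables covered include "treatment utilization (UTQ and app-derived utilization metrics), adverse events, service utilization (obtained from electronic medical record and CSI-SF), and suicidal behaviors".

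Two of these are defined as counts under Measures:

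- **App Use:** "Data on app utilization (e.g., number of times accessed) will also be collected via the app".
- **Service Utilization:** the record query yields "the number of encounters recorded for ER visits, outpatient behavioral health, and inpatient behavioral health (including length of stay").

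Research Design (Sampling) sets the sample at four. Anyone lost before a first treatment session is replaced, so the treated target stays at four.

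No section provides for a median, a range, a listing of individual values, or the number of participants with any event. The plan also does not assign each listed variable to one of its two summaries.

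**The concern.** The study is descriptive, and the Power Analysis says it is not powered for significance. No model or test follows, so the summaries are the result.

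Aim 1 states "We expect that participants will continue to engage with the treatment after discharge via the SmartPhone App", judged in part by app-recorded use. Aim 2 states "We predict that descriptive data will show low levels of suicidal behavior and psychiatric readmission over follow-up". Both are about how many people did something. A mean over four people does not answer that directly, and a count variable has no upper limit to restrain a single large value. A report of mean app use could therefore describe one person rather than the group.

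**Working it through.** **Inputs.** From the documents: n = 4; mean and SD for quantitative data. The plan gives no expected counts, so there is no figure of its own to reproduce. All count values below are assumed for illustration. SD uses the n − 1 divisor.

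**Weight of one person.** Each participant contributes 1/n = 1/4 = 25% of the mean.

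**Example 1: app accesses 5, 8, 10, 90.**
- Sum = 113; mean = 113/4 = 28.25.
- Squared deviations: 540.56 + 410.06 + 333.06 + 3813.06 = 5096.75; SD = √(5096.75/3) = 41.2.
- Median = (8 + 10)/2 = 9. Mean of the three lighter users = 23/3 = 7.7. The heaviest user supplies 90/113 = 80% of all accesses.

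**Example 2: moving only the largest value.** Start from 2, 3, 4, 5 and change the last value. The median is 3.5 and the mean of the other three is 3.0 in every row.

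| Largest value | Mean | SD |
|---|---|---|
| 5 | 3.5 | 1.3 |
| 20 | 7.25 | 8.5 |
| 60 | 17.25 | 28.5 |
| 100 | 27.25 | 48.5 |

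**Example 3: encounters 0, 0, 0, 6.** Mean = 6/4 = 1.5. SD = √((3 × 1.5² + 4.5²)/3) = √(27/3) = 3.0. Median = 0, and one of four had any encounter.

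**Do mean and SD show how many engaged?** Keep the sum (113) and sum of squares (25 + 64 + 100 + 8100 = 8289) of Example 1, but let two participants have zero accesses. The other two values x and y then satisfy x + y = 113 and xy = (113² − 8289)/2 = 2240. So x, y = 56.5 ± √(56.5² − 2240) = 56.5 ± 30.9, about 26 and 87. For 0, 0, 26, 87 the mean is 28.25 and the SD is √((8245 − 4 × 28.25²)/3) = 41.0. These are almost the same mean and SD as in Example 1 (28.25 and 41.2), yet two of four opened the app instead of four of four.

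**How likely is dominance?** This depends on the dispersion, which the documents do not give. In 200,000 simulated samples of four per setting, the proportion in which one participant supplied more than half of all accesses was:

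| Assumed distribution | Proportion |
|---|---|
| Negative binomial, k = 0.5, mean 10 or 30 | about 73% |
| Negative binomial, k = 1, mean 10 or 30 | 51–52% |
| Negative binomial, k = 2, mean 10 or 30 | 27–30% |
| Poisson, mean 10 | 0.2% |

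**The case against.** The best defence has five parts.

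- **The plan offers frequencies too.** It never assigns variables to summaries, so adverse events, suicidal behaviors and readmissions may well be reported as frequencies, which could already give the number with any event. This stands. A reader might infer that every listed variable will get mean and SD, but the text does not say so.
- **The skew is assumed.** A reader might also infer that one large value is typical, or that mean minus SD must fall below zero. Neither is supported: 2, 3, 4, 5 gives 3.5 − 1.3 = 2.2, and the simulated risk of dominance runs from 0.2% to 73%. What stands is that one user can dominate, not that one will.
- **The SD warns the reader.** For four non-negative values SD/mean cannot exceed √4 = 2, and it reaches 2 only when one value alone is non-zero. Mean 1.5 with SD 3.0 therefore identifies 0, 0, 0, 6. This stands in that limiting case. Short of it, the SD signals skew but not how many engaged, as 5, 8, 10, 90 against 0, 0, 26, 87 shows.
- **The stakes are limited.** Aim 2 labels ED and outpatient visits exploratory. Aim 1 also draws on the Utility of Techniques questionnaire, whose frequency categories are bounded. No threshold or test attaches to the counts. All of this stands and keeps the point minor.
- **Authors can add medians or listings when reporting.** True, but the plan does not commit them to it.

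**Conclusion.** The point holds as a minor one. Where mean and SD are used for counts in four people, one participant can set the reported figure. In the assumed example the mean is 28.3 against a median of 9, and the summary does not state how many participants engaged or were readmitted.

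It is clearest for app accesses and length of stay. It extends to encounter counts if they are treated as quantitative, which the plan leaves open. It rests on n = 4, which is stated, and on unequal use across participants, which is plausible but not given.

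A reader might go further and infer that the planned summaries will reverse the conclusions of Aims 1 and 2. The documents do not support that: the SD is reported alongside the mean, other measures inform engagement, and no decision rule depends on these counts.

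**What to change.** Add one sentence to the Analytic Plan: app accesses, encounter counts and length of stay will be summarised by median and range and by the number of participants with at least one access or encounter, with the four individual values shown where a disclosure check allows. Keep mean and SD for scale scores. The same sentence would settle which summary these variables receive.

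The cost is that sentence. No new data, visits or participants are needed. Listing individual values for four young inpatients carries a small re-identification risk; if the check fails, median, range and number with any event largely avoid it and still make most of the gain.

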The Importance of Integrating Technology-Based Interventions into Young Adult Suicide Prevention. Suicidal individuals, particularly younger patients, can be quite challenging to engage and retain in interventions (Kurz & Moller, 1984). For example, rates of dropout and treatment refusal among suicidal adolescents are a substantial concern (Rotheram-Borus et al., 2000) including in studies of BCBT (Sinyor et al., in press). In order to adapt the protocol to enhance engagement of young adults, we propose to use a BCBT app in conjunction with one-on-one treatment sessions. Younger cohorts are highly familiar and comfortable with the use of internet and phone-based applications (Subrahmanyam & Lin, 2007) and use electronic devices for about 7.5 hours per day on average (Rideout et al., 2010). They further demonstrate a preference for technology-based over talk-based psychological interventions (King et al., 2006). One previous study included use of an app in a suicide prevention treatment for adolescent inpatients (Kennard et al., 2018). In that study, treatment was comprised of a 3-hour intervention delivered on the inpatient unit reviewing CBT skills including safety planning (an intervention specifically targeting reducing suicide behaviors) as well as emotion regulation skills designed to improve psychiatric symptoms more generally. Following discharge, participants continued using the app for 24 weeks, rating their mood daily and receiving suggestive feedback for skill use. Results demonstrated that adolescents utilized the app and reported high levels of treatment

satisfaction. In addition, retention through the 24-week follow-up was excellent (88%). However, there were no significant differences between CBT and supportive therapy in terms of satisfaction or clinical outcomes. This limited treatment effect found by Kennard and colleagues (2018) may have been due to the intervention focusing more heavily on regulation of emotional distress as opposed to suicide prevention skills specifically. The current proposal will target the core suicide prevention treatment components from BCBT, a treatment program with prior empirical validation.

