Treatment. Four sessions of BCBT will be delivered by a study therapist using the same study protocol as in our ongoing RCT while also integrating use of a SmartPhone App. The app platform includes interactive features designed to support clinicians caring for patients with suicidality. It also contains patient-facing features (e.g., crisis response planning) used to teach patients suicide prevention skills. Specifically, the app is designed to help patients identify and change unhelpful ways of thinking and behaving while also teaching them effective problem-solving techniques. The app contains 12 sessions which are completed (after an initial introductory therapist-directed session) by the patient in a self-directed way. In the current study we will be using a 4-session version of the app (called OTX-209). App sessions will be completed in collaboration with the study therapist. During treatment sessions participants will use the app to supplement psychoeducation (e.g., watch educational videos) and create digital versions of individualized suicide prevention materials (e.g., crisis response plans). Between sessions and over the follow-up period the participant will interact with the app independently during which time they will be able to review psychoeducation and treatment materials, utilize functions on the app to facilitate skills practice (e.g., a deep breathing visualization exercise) and make edits (e.g., change contacts on the crisis response plan). The app is not monitored so no alert is created based on how the participant uses the app. The consent document informs participants that the app is not monitored and during the informed consent process participants will be verbally reminded that study personnel are not available for emergency needs. If all four sessions are not completed during the inpatient stay the patient will still have access to the remaining sessions on the app and may complete them independently if they choose to do so. The app is experimental and has not been used for this purpose with this content with this population. This is a new procedure/device treatment combination provided in addition to standard of care. Given that the app content is based on empirically-supported BCBT there is no reason to expect untoward outcomes, though this is part of the research question.

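### Does leaving discontinuation out of the analysis list mean that one of Aim 1's two tolerability measures will go unreported?

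*Combined protocol and SAP*

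**What the plan says.** Specific Aims/Hypotheses, Aim 1, commits the study to two tolerability measures: "Tolerability will be assessed using rates of discontinuation and adverse events". It adds that the predictions for this aim rest on descriptive data.

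The Analytic Plan, in the Statistical Analysis Plan section, gives one sentence of variables for descriptive summary. It includes "recruitment and retention rates, implementation barriers, CSQ, treatment utilization (UTQ and app-derived utilization metrics), adverse events", then service utilization and suicidal behaviors. Discontinuation is not named there, nor is the number of sessions completed. The word discontinuation occurs only in Aim 1, and neither it nor retention is defined.

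Four other places bear on the point:

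- Sampling: "We will enroll 4 young adults (ages 18-24) admitted for inpatient treatment", with the rule that "if there is attrition prior to completing at least one treatment session we will continue to enroll additional participants until we meet this target sample". The same section makes an expected stay long enough for the full treatment an entry criterion.
- Treatment: four sessions are planned, and "If all four sessions are not completed during the inpatient stay the patient will still have access to the remaining sessions on the app".
- Procedure: the number of sessions is capped at four and depends on length of stay. For a patient who leaves before the discharge assessment, "the assessment will be completed by phone and remote data collection as will be done for all follow-up assessments".
- Treatment Acceptability and Implementation: a compliance form is "rated by the study therapist at the conclusion of each study treatment session". This form is not in the analysis list.

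**The concern.** An aim names a measure and the analysis list does not carry it. Adverse events, the other half of tolerability, are listed, so the omission looks like an oversight with consequences.

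The nearest listed item, retention, may not fill the gap. The Literature and Background section uses the noun once, for an earlier app study, where it means remaining through follow-up (88% over 24 weeks). In this trial follow-up is remote for everyone, so a patient could leave hospital after one session, answer every survey and count as retained. The sampling rule guarantees only one session per counted participant.

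Two things would then be at stake. Aim 1 predicts good tolerability, and the listed statistics might not show whether patients stopped treatment. The Aim 2 effect sizes would also be hard to read without knowing whether they followed one session or four.

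**Working it through.** The plan states no figure to reproduce: the sample size is a feasibility choice with no power calculation. The check is a count, followed by a comparison of the relevant sections.

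**Inputs.** Target sample 4 (Sampling). Planned sessions per participant 4 (Treatment). Minimum sessions per counted participant 1 (Sampling, replacement rule).

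**Sessions.** Planned total = 4 × 4 = 16. Minimum for the counted sample = 4 × 1 = 4, which is 4/16 = 25%. Maximum = 16/16 = 100%.

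**Retention under each reading, assuming all four answer the follow-ups.**

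| Sessions per participant | Delivered | Retention, read as follow-up | Fewer than four sessions |
|---|---|---|---|
| 1, 1, 1, 1 | 4/16 = 25% | 4/4 = 100% | 4/4 |
| 2, 2, 2, 2 | 8/16 = 50% | 4/4 = 100% | 4/4 |
| 4, 4, 4, 1 | 13/16 = 81% | 4/4 = 100% | 1/4 = 25% |
| 4, 4, 4, 4 | 16/16 = 100% | 4/4 = 100% | 0/4 |

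On the follow-up reading, retention does not separate these rows. If it means completing treatment, the third row gives (4 − 1)/4 = 75%, and retention carries the same information as the last column. So the arithmetic of the worry is right, but only on one of two readings.

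**Which reading?** The text does not decide. The background figure of 88% is about follow-up. The same background section, however, opens by describing suicidal patients as hard to keep in treatment and illustrates this with dropout and refusal; there, retaining someone means retaining them in treatment. The only statement on attrition in this trial itself, the Sampling rule quoted above, is also tied to treatment sessions.

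**Is a low session count discontinuation?** Not necessarily. A patient discharged early has had a short course without choosing to stop, and may finish the sessions alone on the app. The last column is therefore an upper limit on discontinuation by choice. Session count is a separate quantity, and Aim 1 does not name it as a measure.

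**How likely is the first row?** It is a bounding case. Besides the length-of-stay criterion, the Procedure section allows two sessions in one day, a skills review folded into whichever session is last, and extra meetings for unfinished material.

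**Denominator.** If k people are replaced before session 1 and the four treated are all retained, retention is 4/4 among those treated and 4/(4 + k) among all enrolled: 4/5 = 80% for k = 1 and 4/6 = 67% for k = 2 (k is assumed). For k = 0, which the Sampling section expects, the two agree.

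**The case for a change.** The best argument for amending the plan is that the relevant data will exist and the list does not call for them. The compliance form marks each session, but it is not among the analysed variables. The barriers log records obstacles, the techniques questionnaire records use of skills, and the one example given of an app metric is the number of times it was opened. None of these is a session count. Session content also differs: counselling on access to lethal means, which the protocol treats as essential, comes in Session 3. Whether a four-session inpatient treatment could be delivered is a central result for a feasibility trial, and to say that the investigators will probably report it is not to have planned it.

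Part of this stands. Retention and discontinuation should have been defined, and a reader of the results will want to know which sessions each participant received. But the argument shows missing detail, not a faulty rule. The Aim 1 sentence belongs to the same document as the analysis list and already says that the rate will be used. A list that fails to repeat a term does not withdraw it. The barriers log covers logistical obstacles to treatment, including participant availability, and app sessions are worked through with the therapist, so short delivery is unlikely to pass unseen. A session listing would be useful, but it adds to what Aim 1 promises. Counting forms would not give a clean figure from 0 to 4 either, because one session may span several meetings and material may be condensed; a listing by session number would be needed.

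**Conclusion.** No change to the plan follows. The omission is real: discontinuation is named in Aim 1, absent from the analysis list and undefined. An analyst following the combined document would still report how many of the four stopped treatment, because Aim 1 says so and the statistic is a simple proportion. With four participants one person moves that rate by 1/4 = 25 percentage points, so it will be read patient by patient, with the reason for stopping beside it, whatever the list says.

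The spread from 25% to 100% of planned sessions at 100% retention is arithmetically correct. It requires that retention mean follow-up only, that all four answer every follow-up and, at the lower end, that all four stop after one session despite the entry criterion on length of stay. The denominator question arises only if someone is replaced.

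This conclusion assumes that the Aim 1 commitment is honoured in the report and that session attendance can be recovered from the treatment records. Nothing in the documents suggests otherwise. The trial tests no hypothesis and sets no numerical threshold for tolerability, so no decision in the plan depends on how the two terms are defined.
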